5.1 Agent Administration

Treatment will be administered on an outpatient basis according to the regimen table below. Reported adverse events and potential risks are described in Section [7](#). Administration of atezolizumab will be performed in a setting with emergency management capabilities and staff

who are trained to monitor for and respond to medical emergencies.

There will be no dose reduction for atezolizumab in this study. Appropriate dose delays are described in Section 6. No investigational or commercial agents or therapies other than those described below may be administered with the intent to treat the patient's malignancy.

Regimen Description				
Atezolizumab	Dose	Route	Schedule	Cycle Length
Adults ≥ 18 yrs	1200 mg	IV	Day 1, week 1	21 days
Pediatrics ≥ 2 yrs	15 mg/kg (1200 mg max)	IV	Day 1, week 1	21 days

For anaphylaxis precautions, see the management guidelines. Atezolizumab infusions will be administered per the instructions outlined in the table below:

Administration of First and Subsequent Atezolizumab Infusions

First Infusion	Subsequent Infusions

 No premedication is permitted prior to the atezolizumab infusion. Vital signs (pulse rate, respiratory rate, blood pressure, and temperature) should be measured within 60 minutes prior to the infusion. Atezolizumab should be infused over 60 (± 15) minutes. If clinically indicated, vital signs should be measured every 15 (± 5) minutes during the infusion and at 30 (± 10) minutes after the infusion. Patients should be informed about the possibility of delayed post-infusion symptoms and instructed to contact their study physician if they develop such symptoms. 	
 If the patient experienced an infusion-related reaction with any previous infusion, premedication with antihistamines, antipyretics, and/or analgesics may be administered for subsequent doses at the discretion of the investigator. Vital signs should be measured within 60 minutes prior to the infusion. Atezolizumab should be infused over 30 (± 10) minutes if the previous infusion was tolerated without an infusion-related reaction, or 60 (± 15) minutes if the patient experienced an infusion-related reaction with the previous infusion. If the patient experienced an infusion-related reaction with the previous infusion or if clinically indicated, vital signs should be measured during the infusion and at 30 (± 10) minutes after the infusion.

For anaphylaxis precautions, use the following procedure:

Equipment Needed

- Monitoring devices: ECG monitor, blood pressure monitor, oxygen saturation monitor, and thermometer
- Oxygen

- Epinephrine for subcutaneous, intravenous, and/or endotracheal use in accordance with standard practice
- Antihistamines
- Corticosteroids
- IV infusion solutions, tubing, catheters, and tape

Procedures

In the event of a suspected anaphylactic reaction during atezolizumab infusion, the following procedures should be performed:

1. Stop the study drug infusion.
2. Call for additional medical assistance.
3. Ensure that appropriate monitoring is in place, with continuous ECG and pulse oximetry monitoring, if possible.
4. Administer antihistamines, epinephrine, or other medications as required by patient status and directed by the physician in charge.
5. Continue to observe the patient and document observation.
6. Draw serum/plasma samples for immunogenicity testing.
7. Ask participant to return for washout immunogenicity sample if appropriate.

Atezolizumab Dose Preparation

The prescribed dose of atezolizumab should be diluted in 0.9% NaCl to a concentration between 3.2 mg/mL and 16.8 mg/mL and infused through a 0.2 or 0.22 micrometer in-line filter. The IV bag may be constructed of polyvinyl chloride (PVC), polyolefin (PO), polyethylene (PE), or polypropylene (PP); the IV infusion line may be constructed of PVC, PE, or polybutadiene (PB); and the 0.2 or 0.22 micrometer in-line filter may be constructed of polyethersulfone (PES) or polysulfone (PSU). The prepared solution may be stored at 2°C–8°C for up to 24 hours or at ambient < 25°C (77°F) for 8 hours. If the dose solution is stored at 2°C–8°C (36°F–46°F), it should be removed from refrigeration and allowed to reach room temperature prior to administration. This time includes storage and time for administration for infusion. Do not shake or freeze infusion bags containing the dose solution.

5.2 General Concomitant Medication and Supportive Care Guidelines

Because there is a potential for interaction of atezolizumab with other concomitantly administered drugs, the case report form must capture the concurrent use of all other drugs, over-the-counter medications, or alternative therapies. The Principal Investigator should be alerted if the patient is taking any agent known to affect or with the potential for drug interactions. The study team should check a frequently-updated medical reference for a list of drugs to avoid or minimize use of. [Appendix B](#) (Patient Drug Information Handout and Wallet Card) is available.

Palliative radiotherapy to non-targeted lesions may be permitted for patients receiving atezolizumab after completing 2 cycles of therapy and achieving stable or responding disease, at the Principal Investigator's discretion.

Drugs to be avoided:

- Traditional herbal or homeopathic or natural medicines should be limited and used at the discretion of the investigator
- Ingredients for such medicines have not been fully studied, and their use may result in unanticipated drug-drug interactions that may cause or confound assessment of toxicity.
- Immunostimulatory agents, including but not limited to interferon (IFN)- α , IFN- γ , anti-TNF- α , or IL-2 (aldesleukin) (prohibited prior to and during the study and for 10 weeks after the last dose of atezolizumab; see Section [3.2.4](#)). These agents, in combination with atezolizumab, could potentially increase the risk for autoimmune conditions.
- Immunosuppressive medications, including but not limited to cyclophosphamide, azathioprine, methotrexate, and thalidomide. These agents could potentially alter the activity and the safety of atezolizumab.
- Live vaccines and live, attenuated vaccines (prohibited during the study and for 100 days after the last dose of study drug).
- Initiation of granulocyte colony-stimulating factors (e.g., filgrastim and biosimilar products, sargramostim, and/or pegfilgrastim) should be discussed with the Medical Monitor.

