3.2 Exclusion Criteria

- 3.2.1 Any prior therapy must have been completed ≥ 4 weeks or, if known, ≥ 5 half-lives of the prior agent (whichever is shorter) prior to enrollment on protocol (minimum of 1 week between prior therapy and study enrollment), and the participant must have recovered to eligibility levels from prior toxicity. Patients should be at least 6 weeks out from nitrosoureas and mitomycin C. Prior definitive radiation should have been completed ≥ 4 weeks or palliative radiation should have been completed ≥ 2 weeks prior to study enrollment and all associated toxicities resolved to eligibility levels (patients on study may be eligible for palliative radiotherapy to non-targeted lesions after 2 cycles of therapy at the PI's discretion). Patients who have had prior monoclonal antibody therapy must have completed that therapy ≥ 6 weeks (or 3 half-lives of the antibody, whichever is shorter) prior to enrollment on protocol (minimum of 1 week between prior therapy and study enrollment). A patient who has received a cumulative dose of >350 mg/m² of anthracycline (regardless of cardioprotectant) may only be enrolled if their

ejection fraction measured by an echocardiogram is within normal institutional limits.

- 3.2.2 Prior treatment with anti-PD-1, or anti-PD-L1 therapeutic antibody or pathway-targeting agents.
- Patients who have received prior treatment with anti-CTLA-4 may be enrolled, provided the following requirements are met:
 - Minimum of 12 weeks from the first dose of anti-CTLA-4 and >6 weeks from the last dose
 - No history of severe immune-related adverse effects from anti-CTLA-4 (NCI CTCAE Grade 3 and 4)
- 3.2.3 Treatment with any other investigational agent within 4 weeks (or within five half-lives of the investigational product, whichever is shorter) prior to Cycle 1, Day 1 (minimum of 1 week between prior therapy and study enrollment). Patients must be ≥ 2 weeks since any investigational agent administered as part of a Phase 0 study (also referred to as an “early Phase I study” or “pre-Phase I study” where a sub-therapeutic dose of drug is administered) at the Coordinating Center PI’s discretion, and should have recovered to eligibility levels from any toxicities.
- 3.2.4 Treatment with systemic immunostimulatory agents (including, but not limited to, interferon- α or interleukin-2 [aldesleukin]) within 6 weeks prior to Cycle 1, Day 1.

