- 3.2.5 Treatment with systemic immunosuppressive medications (including, but not limited to, prednisone [>10 mg/day], cyclophosphamide, azathioprine, methotrexate, thalidomide, and anti-tumor necrosis factor [anti-TNF] agents) within 2 weeks prior to Cycle 1, Day 1.
- Patients who have received acute, low dose, systemic immunosuppressant medications (e.g., a one-time dose of dexamethasone for nausea) may be enrolled.
 - The use of inhaled corticosteroids and systemic mineralocorticoids (e.g., fludrocortisone) for patients with orthostatic hypotension or adrenocortical insufficiency is allowed.
- 3.2.6 Patients taking bisphosphonate therapy for symptomatic hypercalcemia. Use of bisphosphonate therapy for other reasons (e.g., bone metastasis or osteoporosis) is allowed.
- 3.2.7 Known hypersensitivity to Chinese hamster ovary cell products or other recombinant human antibodies.
- 3.2.8 History of severe allergic, anaphylactic, or other hypersensitivity reactions to chimeric or humanized antibodies (i.e., antibodies with generic names ending in “ximab” or “zumab”, respectively) or fusion proteins
- 3.2.9 Uncontrolled intercurrent illness including, but not limited to, ongoing or active infection, symptomatic congestive heart failure, unstable angina pectoris, cardiac

arrhythmia, or psychiatric illness/social situations that would limit compliance with study requirements.

- 3.2.10 Pregnant women are excluded from this study because atezolizumab is an investigational agent with the unknown potential for teratogenic or abortifacient effects. Because there is an unknown but potential risk for adverse events in nursing infants secondary to treatment of the mother with atezolizumab, breastfeeding should be discontinued if the mother is treated with atezolizumab.
- 3.2.11 Patients with a history of HIV-positive on antiretroviral therapy are eligible with an undetectable viral load. For these patients, an HIV viral load test must be completed within 28 days prior to enrollment.
- 3.2.12 Known clinically significant liver disease, including active viral, alcoholic, or other hepatitis; cirrhosis; fatty liver; and inherited liver disease.
- Patients with past or resolved hepatitis B infection (defined as having a negative hepatitis B surface antigen [HBsAg] test and a positive anti-HBc [antibody to hepatitis B core antigen] antibody test) are eligible. For these patients, HBsAg and anti-HBc tests must be done within 28 days prior to enrollment.

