Pulmonary event, Grade 1	
 Continue atezolizumab and monitor closely. Re-evaluate on serial imaging. Consider patient referral to pulmonary specialist.
Pulmonary event, Grade 2	
 Withhold atezolizumab for up to 12 weeks after event onset.^a

Event	Management
	
 ● Refer patient to pulmonary and infectious disease specialists and consider bronchoscopy or BAL. ● Initiate treatment with corticosteroids equivalent to 1–2 mg/kg/day oral prednisone. ● If event resolves to Grade 1 or better, resume atezolizumab.^b ● If event does not resolve to Grade 1 or better while withholding atezolizumab, permanently discontinue atezolizumab. ● For recurrent events, treat as a Grade 3 or 4 event.
Pulmonary event, Grade 3 or 4	
 ● Permanently discontinue atezolizumab. ● Bronchoscopy or BAL is recommended. ● Initiate treatment with corticosteroids equivalent to 1–2 mg/kg/day oral prednisone. ● If event does not improve within 48 hours after initiating corticosteroids, consider adding an immunosuppressive agent. ● If event resolves to Grade 1 or better, taper corticosteroids over ≥1 month.

BAL = bronchoscopic alveolar lavage

^a Atezolizumab may be withheld for a longer period of time (*i.e.*, >12 weeks after event onset) to allow for corticosteroids (if initiated) to be reduced to the equivalent of ≤10 mg/day oral prednisone. The acceptable length of the extended period of time must be determined by the investigator and the Medical Monitor.

^b If corticosteroids have been initiated, they must be tapered over ≥1 month to the equivalent of ≤10 mg/day oral prednisone before atezolizumab can be resumed.

Hepatic events

Immune-mediated hepatitis has been associated with the administration of atezolizumab. Eligible patients must have adequate liver function, as manifested by measurements of total bilirubin and hepatic transaminases, and liver function will be monitored throughout study treatment. Management guidelines for hepatic events are provided in the table below.

Patients with right upper-quadrant abdominal pain and/or unexplained nausea or vomiting should have liver function tests (LFTs) performed immediately and reviewed before administration of the next dose of study drug.

For patients with elevated LFTs, concurrent medication, viral hepatitis, and toxic or neoplastic etiologies should be considered and addressed, as appropriate.

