^a Atezolizumab may be withheld for a longer period of time (*i.e.*, >12 weeks after event onset) to allow for corticosteroids (if initiated) to be reduced to the equivalent of ≤10 mg/day oral prednisone. The acceptable length of the extended period of time must be determined by the investigator.

^b If corticosteroids have been initiated, they must be tapered over ≥1 month to the equivalent of ≤10 mg/day oral prednisone before atezolizumab can be resumed.

Immune-Mediated Myositis

Immune-mediated myositis has been associated with the administration of atezolizumab. Myositis or inflammatory myopathies are a group of disorders sharing the common feature of inflammatory muscle injury; dermatomyositis and polymyositis are among the most common disorders. Initial diagnosis is based on clinical (muscle weakness, muscle pain, skin rash in dermatomyositis), biochemical (serum creatine kinase increase), and imaging (electromyography/MRI) features, and is confirmed with a muscle biopsy.

Patients with signs and symptoms of myositis, in the absence of an identified alternate etiology, should be treated according to the guidelines in table below.

Event	Management
Immune-mediated myositis, Grade 1	
 Continue atezolizumab. Refer patient to rheumatologist or neurologist. Initiate treatment as per institutional guidelines.
Immune-mediated myositis, Grade 2	
 Withhold atezolizumab for up to 12 weeks after event onset^a and contact Medical Monitor. Refer patient to rheumatologist or neurologist.

Event	Management
	
 • Initiate treatment as per institutional guidelines. • Consider treatment with corticosteroids equivalent to 1–2 mg/kg/day IV methylprednisolone and convert to 1–2 mg/kg/day oral prednisone or equivalent upon improvement. • If corticosteroids are initiated and event does not improve within 48 hours after initiating corticosteroids, consider adding an immunosuppressive agent. • If event resolves to Grade 1 or better, resume atezolizumab.^b • If event does not resolve to Grade 1 or better while withholding atezolizumab, permanently discontinue atezolizumab and contact Medical Monitor.

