Immune-mediated reactions may involve any organ system and may lead to hemophagocytic lymphohistiocytosis (HLH) and macrophage activation syndrome (MAS).

Patients with suspected HLH should be diagnosed according to published criteria by McClain and Eckstein (2017). A patient should be classified as having HLH if five of the following eight criteria are met:

- Fever $\geq 38.5^{\circ}\text{C}$
- Splenomegaly
- Peripheral blood cytopenia consisting of at least two of the following:
 - Hemoglobin < 90 g/L (9 g/dL) (< 100 g/L [10 g/dL] for infants < 4 weeks old)
 - Platelet count $< 100 \times 10^9/\text{L}$ (100,000/mcL)
 - ANC $< 1.0 \times 10^9/\text{L}$ (1000/mcL)
- Fasting triglycerides > 2.992 mmol/L (265 mg/dL) and/or fibrinogen < 1.5 g/L (150 mg/dL)
- Hemophagocytosis in bone marrow, spleen, lymph node, or liver
- Low or absent natural killer cell activity
- Ferritin > 500 mg/L (500 ng/mL)
- Soluble interleukin 2 (IL-2) receptor (soluble CD25) elevated ≥ 2 standard deviations above age-adjusted laboratory-specific norms

Patients with suspected MAS should be diagnosed according to published criteria for systemic juvenile idiopathic arthritis by Ravelli *et al.* (2016). A febrile patient should be classified as having MAS if the following criteria are met:

- Ferritin > 684 mg/L (684 ng/mL)
- At least two of the following:
 - Platelet count $\leq 181 \times 10^9/\text{L}$ (181,000/mcL)
 - AST ≥ 48 U/L
 - Triglycerides > 1.761 mmol/L (156 mg/dL)
 - Fibrinogen ≤ 3.6 g/L (360 mg/dL)

Patients with suspected HLH or MAS should be treated according to the guidelines in below.

Event	Management
Suspected HLH or MAS	
 ● Permanently discontinue atezolizumab and contact Medical Monitor. ● Consider patient referral to hematologist. ● Initiate supportive care, including intensive care monitoring if indicated per institutional guidelines. ● Consider initiation of IV corticosteroids and/or an immunosuppressive agent. ● If event does not improve within 48 hours after initiating corticosteroids, consider adding an immunosuppressive agent. ● If event resolves to Grade 1 or better, taper corticosteroids over ≥ 1 month.

HLH= hemophagocytic lymphohistiocytosis; MAS= macrophage activation syndrome.

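### Section 5.2 lists anti-TNF-alpha as immunostimulatory and prohibits it until 10 weeks after the last dose, while 3.2.5 classes it as immunosuppressive; read literally, this removes one class of agent in 11 rows of the 6.2 tables.

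*Combined protocol and SAP*

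**What the plan says.** Four places in the combined protocol and SAP bear on this.

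- **Section 5.2, immunostimulatory bullet.** It names interferon alpha and gamma, anti-TNF-alpha and IL-2. The group is "prohibited prior to and during the study and for 10 weeks after the last dose of atezolizumab", with a cross-reference to 3.2.4. The reason given is: "These agents, in combination with atezolizumab, could potentially increase the risk for autoimmune conditions".
- **Section 5.2, immunosuppressive bullet.** It reads "Immunosuppressive medications, including but not limited to cyclophosphamide, azathioprine, methotrexate, and thalidomide". Anti-TNF is not among the named examples. The bullet falls under the general heading of drugs to avoid, but it does not use the word prohibited and sets no time window.
- **Section 3.2, exclusion criteria.** Criterion 3.2.4 covers immunostimulatory agents; its examples are interferon alpha "or interleukin-2 [aldesleukin]) within 6 weeks prior to Cycle 1, Day 1". Criterion 3.2.5 covers systemic immunosuppressive medications, and its list ends with "anti-tumor necrosis factor [anti-TNF] agents) within 2 weeks prior to Cycle 1, Day 1".
- **Section 6.2, management tables.** For severe pulmonary events, and in similar words for several others, the instruction is: "If event does not improve within 48 hours after initiating corticosteroids, consider adding an immunosuppressive agent". The suspected HLH/MAS row carries the same step and also says: "Consider initiation of IV corticosteroids and/or an immunosuppressive agent".

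**The concern.** One drug class carries opposite labels in two sections, and the label decides which rule applies. Under 5.2 as written, anti-TNF faces an express prohibition with a stated duration. Had it been listed with cyclophosphamide and azathioprine, it would face only a general caution with no window. Misplacement therefore puts it under a stricter rule than the agents that 3.2.5 groups it with.

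The rule matters when a serious event has failed to improve on corticosteroids and the investigator is told to think about adding an immunosuppressive agent. A site reading 5.2 to the letter would regard one such class as closed. A site that used it would contravene an explicit prohibition while following the spirit of 6.2. In a multicentre trial, sites may resolve this differently.

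**Working it through.** The plan states no figure to reproduce. The check is a comparison of text, a count of table rows and one conversion of units.

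**1. Classification.**

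| Section | Label for anti-TNF | Rule attached |
|---|---|---|
| 5.2, immunostimulatory bullet | immunostimulatory | prohibited before and during the study and for 10 weeks after the last dose |
| 3.2.4 (cited by 5.2) | not named | 6-week wash-out for immunostimulatory agents |
| 3.2.5 | immunosuppressive | 2-week wash-out |
| 5.2, immunosuppressive bullet | not named | to be avoided; no window |

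The cross-reference does not support the placement, and the only other section that names the class contradicts it. Criterion 3.2.5 lists prednisone, cyclophosphamide, azathioprine, methotrexate, thalidomide and anti-TNF. The immunosuppressive bullet of 5.2 repeats the middle four in the same order, and anti-TNF appears one bullet higher. That pattern suggests a misplaced term, not a chosen policy.

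**2. Rows of 6.2 with the 48-hour step to consider an immunosuppressive agent.**

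| Event type | Grade rows | Rows | Atezolizumab |
|---|---|---|---|
| Pulmonary | 3 or 4 | 1 | discontinued |
| Hepatic | 3 or 4 | 1 | discontinued |
| Diarrhea or colitis | 4 | 1 | discontinued |
| Myocarditis | 3-4 | 1 | discontinued |
| Pancreatitis | 4 | 1 | discontinued |
| Meningoencephalitis | all | 1 | discontinued |
| Renal | 3 or 4 | 1 | discontinued |
| Myositis | 2; 3 | 2 | withheld, may resume |
| Myositis | 4 | 1 | discontinued |
| Suspected HLH or MAS | not graded | 1 | discontinued |

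Total: 1 + 1 + 1 + 1 + 1 + 1 + 1 + 2 + 1 + 1 = 11 rows over 9 event types (myositis counted once). Permanent discontinuation applies in 9 rows; in 2 rows dosing may resume. The myositis Grade 2 row words the step conditionally: "If corticosteroids are initiated and event does not improve within 48 hours after initiating corticosteroids, consider adding an immunosuppressive agent". None of the 11 rows names anti-TNF or any other agent.

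**3. Timing.** The post-treatment window is 10 weeks x 7 = 70 days. For a patient who stays on study treatment, the ban applies because it runs throughout the study. For a patient discontinued because of the event, assume that the event starts within one 21-day cycle of the last dose. The 48-hour point then falls no later than 21 + 2 = 23 days after that dose, inside the 70 days.

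**4. Is there an exception?** Section 5.2 makes none for treating adverse events. Section 6.2 does not refer to the 5.2 prohibition or lift it.

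**The case against.** The best reply is that 5.2 is general guidance and 6.2 is specific. All immunosuppressives are on the list to avoid, yet 6.2 tells sites to consider them, so the protocol already works only if Section 6 governs. That is a sensible reading for the immunosuppressive bullet. It is weaker for anti-TNF, because the word there is prohibited, and on this drug 5.2 is the specific provision: it names the class and no 6.2 row does. No text says that Section 6 prevails.

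The objections to a larger claim do stand. A reader might infer any of the following, and the documents support none of them.

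- *Section 6.2 cannot be carried out.* A site obeying 5.2 to the letter can still follow every row with another agent.
- *Anti-TNF is the needed or preferred agent.* Nothing says so. Section 6.2 refers management of several events to the Investigator's Brochure, which is not among the documents.
- *The infusion-reaction and cytokine-release rows are also affected.* Grades 2 to 4 mention anti-cytokine therapy, but no agent is named and a footnote says its role there is not established. These rows should not be counted.
- *The ban lasts 90 days, by adding the 5.4 follow-up.* Section 5.4 follows patients removed for adverse events until resolution or stabilization, so 90 days is not the limit for the patients at issue. Only the 10 weeks is stated.
- *The autoimmune rationale is pharmacologically false.* The documents hold no data on anti-TNF given with atezolizumab. They show only that the rationale is attached to a class that 3.2.5 labels the other way.
- *Corticosteroids are caught.* Section 5.2 names none, and 6.1 and 6.2 govern their use.
- *Eligibility is changed, with 6 weeks set against 2.* Criterion 3.2.4 does not name anti-TNF and 3.2.5 does; 3.2.1 and 3.2.13 restrict such patients as well.

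**Conclusion.** The inconsistency is real and lies in an operative rule. By the protocol's own classification in 3.2.5, anti-TNF-alpha is in the wrong bullet of 5.2, under a prohibition that cites a criterion not naming it. Read literally, this closes one immunosuppressive class during treatment and for 70 days after the last dose, where 11 rows over 9 event types call for considering such an agent.

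Those 11 rows mark how far the text reaches. They are not a count of patients or a probability of harm, and the documents allow no estimate of either. The conclusion assumes that a site applies the prohibition as written and treats 3.2.5 as the correct label. Severity is minor: a safety-text correction with no bearing on the response endpoint, the sample size or the error rates of the two-stage design.

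**What to change.** At the next amendment, make two changes in 5.2:

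1. Move anti-TNF-alpha from the immunostimulatory bullet to the immunosuppressive bullet.
2. Add to the immunosuppressive bullet: *Immunosuppressive agents given to manage adverse events under Section 6 are permitted.*

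Both parts are needed. The move alone removes the contradiction with 3.2.5 but leaves anti-TNF on the list of drugs to avoid, with nothing to say that Section 6 treatment is outside it. The cost is one term moved and one sentence added, with no new procedures, data or patients.
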